7.5 Second Manuscript

This paper will report results for dietary patterns (secondary outcome), which includes dietary intake, UPF, and skin carotenoids at 6- and/or 12-months.

Dietary Intake

We will assess group differences in HEFI-2019 total and component scores as continuous outcomes using mixed-effects linear regression. Models will be adjusted for baseline HEFI-2019 total and component scores, and blocking variables (baseline A1C, gender, recruitment location). To improve the precision of effect estimates, models will also be adjusted for age, race/ethnicity, educational attainment, number of children living in the home, marital status, smoking status, dietary recall day (for 2 recalls: 2 weekend days, 2 weekdays, 1 weekend and 1 weekday; for 1 recall: 1 weekend, or 1 weekday), and usual intake (more than usual, usual, less than usual intake). Additionally, all models will include baseline A1C data source (study measured vs administrative health data), and group (FoodRx vs comparison) indicator variables. We will include random intercepts for participants (participant study ID) to account for within-subject correlation due to repeated measures, and for primary care clinics (clinic study ID) to account for clustering of participants within clinics. Missing data for covariates will be addressed using full information maximum likelihood.

We will conduct subgroup analyses for HEFI-2019 scores by baseline household food insecurity severity (marginal, moderate, severe), Indigenous identity (self-identified as First Nations, Inuk, Métis), gender (man, woman, gender diverse), recruitment location (urban setting, rural setting, Indigenous primary care clinic), baseline A1C ($\leq 8.5\%$, $\geq 8.6\%$), and supplement intake.

In addition to per-protocol and as-treated analyses, we will conduct sensitivity analyses for HEFI-2019 scores to examine the impact on dietary patterns when they are assessed using the HEI-2015, and the impact of energy intake misreporting (i.e., reported total energy intake to predicted total energy expenditure) on the HEFI-2019 and HEI-2015 models. We will also calculate pairwise Pearson correlations between HEFI-2019 scores and skin carotenoids.¹²²

Ultra-Processed Foods

We will assess group differences in proportion of energy consumed as UPF as a continuous outcome using mixed-effects linear regression. Models will be adjusted for baseline UPF, and blocking variables (baseline A1C, gender, recruitment location). To improve the precision of effect estimates, models will also be adjusted for age, race/ethnicity, educational attainment, number of children living in the home, marital status, and smoking status. Additionally, all models will include baseline A1C data source (study measured vs administrative health data), and group (FoodRx vs comparison) indicator variables. We will include random intercepts for participants (participant study ID) to account for within-subject correlation due to repeated measures, and for primary care clinics (clinic study ID) to account for clustering of participants within clinics. Missing data for covariates will be addressed using full information maximum likelihood.

In addition to per-protocol and as-treated analyses, we will conduct sensitivity analyses for UPF to examine the impact of energy intake misreporting (i.e., reported total energy intake to predicted total energy expenditure) in UPF models.

Skin Carotenoids

We will assess group differences in skin carotenoids as a continuous outcome using mixed-effects linear regression. Models will be adjusted for baseline skin carotenoid scores, and blocking variables (baseline A1C, gender, recruitment location). To improve the precision of effect estimates, models will also be adjusted for age, race/ethnicity, educational attainment, number of children living in the home, marital status, smoking status, supplement intake, and season of measurement (spring, summer, autumn, winter). Additionally, all models will include baseline A1C data source (study measured vs administrative health data), and group (FoodRx vs

comparison) indicator variables. We will include random intercepts for participants (participant study ID) to account for within-subject correlation due to repeated measures, and for primary care clinics (clinic study ID) to account for clustering of participants within clinics. Missing data for covariates will be addressed using full information maximum likelihood.

In addition to per-protocol and as-treated analyses, we will conduct sensitivity analyses for skin carotenoids to examine the impact on dietary patterns when they are assessed using the HEI-2015.

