3.3 Data Collection Schedule and Data Sources

Participants in both groups completed data collection at baseline (0-months), mid- (6-months), and post-intervention (12-months with data collection beginning 2 weeks prior to participants' program end date). Participants completed a self-administered online questionnaire in REDCap⁴¹, 2 online 24-hour dietary recalls using the Automated Self-Administered 24-Hour Dietary Assessment Tool for Canada (ASA24-2018-Canada)⁴², and biochemical and physical measurements (e.g., blood samples, height, weight, skin carotenoids) as per the schedule in Figure 1.

[figure not shown]

Figure 1: Data Collection Schedule

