3.4 Randomization and Blinding

Prior to randomization, participants completed baseline data collection and received the healthy food prescription. Researchers randomized participants to either the FoodRx (n=299) or comparison (n=297) group with a 1:1 allocation ratio using a computer-generated, concealed, blocked randomization sequence in REDCap (Research Electronic Data Capture)⁴¹ created by an independent statistician. Blocking variables included gender identity (woman, man), recruitment location (urban setting, rural setting, Indigenous primary care clinic), and baseline A1C (6.5-8.5%, 8.6-12%). The intervention group received both a healthy food prescription and a healthy food incentive. The comparison group received a healthy food prescription alone.

Due to the nature of the intervention, participants were not blinded to their allocation; however, they were blinded to study objectives. Participants in the comparison group were also blinded to the details of the healthy food incentive, including its monetary value and eligible foods. Care providers and researchers who collected and analyzed the data were blinded to treatment allocation with the exception of a research assistant who assisted participants in the intervention group throughout the trial.

4. Trial Population

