5.2.3 Dietary Patterns

Healthful dietary patterns are essential for the management of T2DM, and are the mechanism through which A1C improves or declines.⁶² We used both subjective and objective measurements to provide a comprehensive assessment of the quality of participants' dietary patterns.

Dietary Intake We collected self-reported (i.e., subjective) dietary intake data to assess the quality of dietary patterns using the ASA24-2018-Canada online system, which is a modified version of the ASA24 based on the Canadian food supply, portion sizes, and nutrition composition.⁶³ Participants reported all foods, beverages, and supplements consumed from midnight-to-midnight the previous day as well as if their reported intake was more than usual, usual, or less than usual. The system also recorded the date and time for each recall. Participants completed 2 x 24-hour dietary recalls for a total of 6 recalls to better capture the intake of episodically consumed foods and daily variability, thereby, providing more accurate estimates of usual dietary intake.

Prompts to enter a second recall were sent 2-5 days after the first recall, with the specific interval determined at random. Participants entered dietary recalls on any day of the week including weekends (Friday-Sunday). This data will be used to determine recall day and season of measurement, which is defined as spring (March-May), summer (June-August), autumn (September-November), and winter (December-February).

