We will assess group differences in diabetes competing demands as a binary outcome using mixed-effects logistic regression. Models will be adjusted for baseline diabetes competing demands, and blocking variables (baseline A1C, gender, recruitment location). To improve the precision of effect estimates, models will also be adjusted for age, race/ethnicity, educational attainment, annual household income, years lived in Canada, household composition, marital status, and diabetes duration. Additionally, all models will include baseline A1C data source (study measured vs administrative health data), and group (FoodRx vs comparison) indicator variables. We will include random intercepts for participants (participant study ID) to account for within-subject correlation due to repeated measures, and for primary care clinics (clinic study ID) to account for clustering of participants within clinics. Missing data for covariates will be addressed using full information maximum likelihood.

In addition to per-protocol and as-treated analyses, we will conduct sensitivity analyses for diabetes competing demands as described in Section 7.2.

Hypoglycemic Episode Frequency

We will assess group differences in hypoglycemic episode frequency as an ordinal outcome using mixed-effects logistic regression. Models will be adjusted for baseline hypoglycemic episode frequency, and blocking variables (baseline A1C, gender, recruitment location). To improve the precision of effect estimates, models will also be adjusted for age, race/ethnicity, educational attainment, annual household income, years lived in Canada, household composition, marital status, diabetes duration, and physical activity level. Additionally, all models will include baseline A1C data source (study measured vs administrative health data), and group (FoodRx vs comparison) indicator variables. We will include random intercepts for participants (participant study ID) to account for within-subject correlation due to repeated measures, and for primary care clinics (clinic study ID) to account for clustering of participants within clinics. Missing data for covariates will be addressed using full information maximum likelihood.

In addition to per-protocol and as-treated analyses, we will conduct sensitivity analyses for hypoglycemic episode frequency as described in Section 7.2.

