7.9 Sixth Manuscript

This paper will assess for evidence of improvements in trade-offs that might result from reduced food insecurity through the FoodRx intervention. In this paper, we will report results for self-reported medication adherence, physical activity level, and perceived financial barriers to chronic disease care.

Medication Adherence

We will assess group differences in medication adherence as a continuous outcome using mixed-effects linear regression. Models will be adjusted for baseline medication adherence, and blocking variables (baseline A1C, gender, recruitment location). To improve the precision of effect estimates, models will also be adjusted for age, race/ethnicity, educational attainment, annual household income, marital status, number of children living in the home, and diabetes duration.

Additionally, all models will include baseline A1C data source (study measured vs administrative health data), and group (FoodRx vs comparison) indicator variables. We will include random intercepts for participants (participant study ID) to account for within-subject correlation due to repeated measures, and for primary care clinics (clinic study ID) to account for clustering of participants within clinics.

In addition to per-protocol and as-treated analyses, we will conduct sensitivity analyses for medication adherence as described in Section 7.2.

Physical Activity Level

We will assess group differences in physical activity level as a discrete outcome using mixed-effects Poisson regression. Models will be adjusted for baseline physical activity level, and blocking variables (baseline A1C, gender, recruitment location). To improve the precision of effect estimates, models will also be adjusted for age, race/ethnicity, educational attainment, annual household income, marital status, number of children living in the home, BMI, smoking status, and diabetes duration. Additionally, all models will include baseline A1C data source (study measured vs administrative health data), and group (FoodRx vs comparison) indicator variables. We will include random intercepts for participants (participant study ID) to account for within-subject correlation due to repeated measures, and for primary care clinics (clinic study ID) to account for clustering of participants within clinics. Missing data for covariates will be addressed using full information maximum likelihood.

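### The main HEFI-2019 model adjusts for an apparently post-randomisation self-rating of intake, which may bias the estimated effect on diet quality in either direction

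*SAP*

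**What the plan says.** The Dietary Intake part of SAP section 7.5 models HEFI-2019 total and component scores by mixed-effects linear regression. Some terms are tied explicitly to baseline: "Models will be adjusted for baseline HEFI-2019 total and component scores, and blocking variables". A further set is added to improve precision. It ends with recall day, whose categories for one or two recalls are spelled out, "and usual intake (more than usual, usual, less than usual intake". No timepoint is given for this last term, and no rule for combining two ratings.

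Section 5.2.3 says where the rating comes from. In each recall participants reported what they had consumed, "as well as if their reported intake was more than usual, usual, or less than usual". On the number of recalls it states: "Participants completed 2 x 24-hour dietary recalls for a total of 6 recalls".

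The timing follows from two other sections. Section 3.3: "Participants in both groups completed data collection at baseline (0-months), mid- (6-months), and post-intervention". Section 3.4: "Prior to randomization, participants completed baseline data collection and received the healthy food prescription". Section 3.4 also says that participants knew their allocation.

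Section 6.3 commits to intention-to-treat analysis, and section 6.2 to reporting both adjusted and unadjusted estimates.

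**The concern.** Adjusting for precision is sound for covariates fixed before randomisation. A rating made during follow-up, alongside the outcome, is a response that treatment may alter.

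There is a credible route here. Every participant is food insecure at entry (section 4.1), and the programme aims to reduce food insecurity (section 2.1). The module in section 5.2.4 measures this partly through smaller or skipped meals and days without food. Some below-usual recall days may be such days, though the SAP does not say so.

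If the incentive moves the rating and the rating tracks HEFI-2019, the adjusted coefficient leaves out that part of the effect. If illness or appetite, say, influences both the rating and diet quality, conditioning on the rating can also create bias where the rating itself has no effect on the score. At stake is the meaning of the adjusted diet-quality result in the second manuscript. The primary A1C analysis is not affected.

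**Working it through.** **1. When the ratings are made.** Two recalls (section 5.2.3) at three timepoints (section 3.3) give 2 x 3 = 6, which matches the SAP's total. Baseline collection precedes randomisation (section 3.4), so 2 of the 6 ratings are made before randomisation and 4 after. There is one exception. Section 7 says 31 participants were affected by the restart, and those who stayed repeated baseline collection after having been randomised. It is this second baseline that the analyses use.

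**2. Which rating the model uses.** The SAP does not say. Two features of section 7.5 point to the concurrent rating. The HEFI-2019 scores, A1C and A1C data source are labelled as baseline, but this term is not. It also stands next to recall day, which describes the recalls being scored.

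**3. Coding.** For recall day the SAP defines five categories: three for two recalls and two for one recall. The rating has three levels. Two recalls can give 3 matching and 3 differing pairs, and a single recall gives 3 more values. The SAP does not say how the differing pairs are handled.

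**4. How the SAP treats similar terms.** The ultra-processed-food model uses the same recalls but has no usual-intake term (section 7.5). For 12-month A1C, adjustment for medication change after baseline is a sensitivity analysis and not part of the main model (section 7.4).

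**5. What conditioning does.** The SAP states no effect size, variance or rating frequency for HEFI-2019, so there is no figure of its own to reproduce. Simplify the rating to below usual or not, and let

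- T = total effect of allocation on HEFI-2019;
- a = share of below-usual records in the comparison group minus the share in the FoodRx group;
- b = HEFI-2019 points by which a below-usual record scores lower within a group.

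Without an unmeasured common cause, adjusted coefficient = T - a x b.

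Every value that follows is assumed: T = 3 points and a below-usual share of 30% in the comparison group. The common cause is a standard normal variable that correlates 0.5 with the latent rating and adds 4 HEFI-2019 points per SD, with residual SD 9. Each scenario was simulated with 400,000 records and fitted by ordinary least squares, with and without the rating. The simulated columns show the adjusted minus the unadjusted coefficient.

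| a | b | -a x b | Simulated, no common cause | Simulated, common cause |
|---|---|---|---|---|
| 0 | 5 | 0 | -0.01 | -0.01 |
| 0.10 | 0 | 0 | 0.00 | -0.33 |
| 0.10 | 2 | -0.20 | -0.20 | -0.54 |
| 0.10 | 5 | -0.50 | -0.51 | -0.84 |
| 0.20 | 5 | -1.00 | -0.99 | -1.71 |
| -0.10 | 2 | +0.20 | +0.19 | +0.52 |
| -0.10 | 5 | +0.50 | +0.51 | +0.82 |

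The simulation agrees with the formula. With a = 0 nothing is lost. With a positive and b = 5 the effect is attenuated, by up to 1.0 / 3 = one third in the no-common-cause column. With a negative it is inflated. A common cause adds bias even at b = 0, provided that treatment shifts the rating.

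**The case against.** **Certain attenuation is not shown.** A reader might infer that part of the diet effect is adjusted away, towards no effect. That requires the incentive to shift the rating, and the rating to track HEFI-2019 in the matching direction. The SAP shows neither. The rating compares a day with the participant's own norm, whereas HEFI-2019 measures agreement with the food guide. A change sustained for 6 to 12 months may itself be rated usual. In lasting food insecurity, days short of food may be rated usual too. This objection stands against any claim of certainty or direction. It does not remove the problem, because the model depends on an untested assumption that the incentive leaves the rating unchanged.

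**The timepoint is an inference.** This also stands. The SAP could mean the baseline rating, but then it needs to say so, and action is needed on either reading.

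**Unadjusted estimates will be reported, and secondary outcomes are treated as supportive** (sections 6.2 and 6.5). This lowers the stakes. It mitigates only in part: the unadjusted estimate drops the other covariates as well, so it cannot isolate this term, and no sensitivity analysis listed for HEFI-2019 removes the rating.

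**Two other models might seem to share the fault.** The hypoglycaemia model lists "marital status, diabetes duration, and physical activity level" and the physical activity model lists "number of children living in the home, BMI, smoking status, and diabetes duration", so physical activity and BMI enter without a baseline label. The documents do not support reading these as follow-up values. Age, smoking status and marital status also lack the label. Section 4.5 lists neither variable, but it equally omits blood pressure and lipids, which are explicitly adjusted at baseline. Baseline values of both are used elsewhere in section 7. At most this is a wording clarification.

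**Conclusion.** The concern holds as a risk of bias, not as a demonstrated loss of effect. As written, the main HEFI-2019 model apparently conditions on an unblinded self-report collected after randomisation with the outcome, and a precision rationale does not justify that. The adjusted group coefficient therefore may not be the intention-to-treat effect on diet quality.

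The size is unknown and the sign is open. The illustrative shifts (about +0.5 to -1.0 points on a 3-point effect, or +0.8 to -1.7 with a common cause) rest wholly on assumed inputs, a two-level rating and a simple linear model. They show that the bias can be attenuating, inflating or zero, and they do not estimate it. The verdict also rests on reading the covariate as the concurrent rating. Because the outcome is secondary and unadjusted results are promised, the impact is moderate, but the change is worth making.

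**What to change.** In the Dietary Intake part of SAP section 7.5:

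1. Remove usual intake from the main HEFI-2019 model, or state that only the baseline rating is used. If the latter, say which baseline applies to participants who restarted, since their second baseline came after randomisation.
2. Keep recall day, which mainly reflects scheduling and already has defined categories.
3. Report the model with the concurrent rating only as a sensitivity analysis, and define the coding when two recalls carry different ratings and when there is only one recall. This matches how section 7.4 handles medication change after baseline.

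The cost is a few lines of SAP text and possibly a small loss of precision in the HEFI-2019 estimate. No new data are needed.

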We will use this data to assess the alignment of participants' dietary intake with national nutrition guidance by using the appropriate scoring algorithms to calculate Healthy Eating Food Index 2019 (HEFI-2019)^{64, 65} and Healthy Eating Index-2015 (HEI-2015)⁶⁶⁻⁶⁹ scores. The HEFI-2019 is a 10-component index that aligns with the content and objectives of Canada's Food Guide 2019 (CFG-2019). Total HEFI-2019 scores are the sum of individual component scores, and range from 0-80 with higher scores indicating greater adherence to CFG-2019 guidelines.⁶⁴ The HEI-2015 is a 13 component index that sums component scores for adequacy (foods that align with nutritional guidelines) and moderation (foods with suggested limited intake), and a total score, which ranges from 0-100, with higher scores indicating higher adherence to the 2015-2020 Dietary Guidelines for Americans. For each index, scores will be calculated as the mean of two recalls when available; if only one recall is available, a single score will be used. HEFI-2019 and HEI-2015 scores will be analyzed as continuous outcomes.

*Ultra-Processed Foods** We will use dietary intake data collected with the ASA24-2018-Canada to calculate the proportion of energy consumed from ultra-processed foods (UPF), which are manufactured foods and beverages that contain few to no whole foods. All foods and beverages reported in dietary recalls will be classified using the NOVA classification system, which includes definitions and examples.⁷⁰ This system classifies foods and beverages into 4 groups, including unprocessed or minimally processed, processed culinary ingredients,

processed, or ultra-processed. The numerator for each group will be the average energy intake from UPF from both recalls and the denominator for all groups will be the total average daily energy intake from both recalls at each timepoint. UPF will be analyzed as a continuous outcome.

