Skin Carotenoids Notwithstanding their demonstrated validity⁷¹, dietary recalls are subjective self-reports and are prone to reporting errors and bias.⁷² To address these issues, we collected skin carotenoid data to provide objective approximations of vegetable and fruit consumption, which are key components of healthy dietary patterns.⁷³ Carotenoids are phytonutrients only present in food and are abundant in vegetables and fruit. Once consumed, they are stored in both blood and skin. Skin carotenoids are valid and reliable measures of fruit and vegetable intake,⁷⁴ and are positively correlated with plasma carotenoids.⁷⁵ We measured carotenoids dermally using Pharmanex Biophotonic Scanners (NuSkin Enterprises, Provo, UT, USA), which are non-invasive measurements taken through participants' palms. Researchers collected 3 scans for each participant. Each scan provides a score ranging from 10,000 to 80,000, with 10,000 indicating a diet low in carotenoids and 80,000 indicating a diet very high in carotenoids.⁷⁶ Researchers collected 3 scans for each participant. Scores for each participant will be calculated by averaging these 3 measurements. Skin carotenoids will be analyzed as a continuous outcome.

*Supplements** Participants also reported dietary supplement intake in each recall. Evidence suggests consuming supplements containing carotenoids may substantially increase plasma and skin carotenoid levels.^{77,78} We will create a binary indicator variable to capture supplement intake. Intake is defined as consumption of supplements containing beta-carotene, lycopene, lutein, zeaxanthin, alpha-carotene, or gamma-carotene both individually and in combination. No intake is defined as consumption of supplements that do not include the aforementioned carotenoids or supplement consumption was not reported in the dietary recalls. Supplement intake will be included as a covariate to account for potential influence on observed skin carotenoid levels, thereby allowing estimates to better reflect consumed foods.

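### The one outcome-specific sensitivity analysis listed for skin carotenoids re-scores self-reported recalls with HEI-2015, so it cannot test the scan-based result or isolate the supplement threat the SAP names

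*SAP*

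**What the plan says.** SAP section 5.2.3 gives the scan a specific purpose. Because recalls are subjective and error-prone, "we collected skin carotenoid data to provide objective approximations of vegetable and fruit consumption". The outcome is built from three scans: "Scores for each participant will be calculated by averaging these 3 measurements". The two diet indices, HEFI-2019 and HEI-2015, come from the recalls: each is averaged over two recalls, or taken from one if only one exists.

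The same section identifies a threat to the scan: "Evidence suggests consuming supplements containing carotenoids may substantially increase plasma and skin carotenoid levels". The response is a yes/no supplement indicator, derived from the recalls and entered as a covariate. Its *no intake* class covers people who took only supplements without the listed carotenoids, "or supplement consumption was not reported in the dietary recalls".

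In section 7.5, the skin carotenoid model is a mixed-effects linear regression with supplement intake among its covariates. Beyond the per-protocol and as-treated analyses, one sensitivity analysis is listed: "we will conduct sensitivity analyses for skin carotenoids to examine the impact on dietary patterns when they are assessed using the HEI-2015". Earlier in section 7.5, under Dietary Intake, the plan has "sensitivity analyses for HEFI-2019 scores to examine the impact on dietary patterns when they are assessed using the HEI-2015".

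**The concern.** A sensitivity analysis should repeat the estimate for the outcome in question while changing something that the estimate depends on. The HEI-2015 analysis changes nothing on which the carotenoid estimate depends. It produces a second result for diet quality from the self-reports that the scan was collected to supplement.

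The slot matters because the SAP names a concrete competing explanation for a carotenoid difference. If supplement use came to differ between arms, part of an observed difference could reflect supplements and not vegetables and fruit. Elsewhere the SAP gives threats of this kind their own run. In section 7.4 the blood pressure outcomes are repeated without participants who started anti-hypertensive therapy, several lipid outcomes without those who started lipid-lowering therapy, and 12-month A1C with adjustment for medication change. Skin carotenoids have no counterpart.

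**Working it through.** No figure is stated for skin carotenoids or supplement use, so there is nothing to reproduce numerically. The check is a comparison of the passages.

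**Step 1: data sources.** HEI-2015 is scored from 24-hour recalls (5.2.3, Dietary Intake). Skin carotenoids are the mean of three scanner readings (5.2.3, Skin Carotenoids). The two share no raw data. The supplement covariate does come from the recalls, but HEI-2015 scoring does not alter it.

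**Step 2: the two HEI-2015 sentences.** Under HEFI-2019, HEI-2015 is a second index applied to the same recalls, so it tests whether the diet-quality result depends on the choice of index. Under skin carotenoids the wording recurs with only the outcome name changed, and the reference to dietary patterns assessed by HEI-2015 no longer bears on the outcome. Carry-over from the earlier paragraph is the likely explanation, though the SAP cannot confirm it.

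**Step 3: what else covers the scan result, and whether it isolates supplement handling.**

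| Planned analysis | Varies the carotenoid estimate? | Isolates supplement handling? |
|---|---|---|
| HEI-2015 re-scoring (7.5) | No | No |
| Per-protocol and as-treated (7.2) | Yes, through who is analysed and in which group | No |
| Multiple imputation, inverse probability weighting, available case, pattern mixture (6.4) | Yes, through the missing-data assumption | No |
| Unadjusted estimate (6.2) | Yes, on the ordinary reading that all adjustment is removed | No, the supplement term goes together with the other covariates |
| Correlation of HEFI-2019 with the scan (7.5) | No, it is not a comparison of arms | No |
| Subgroups by supplement intake (7.5) | No, they are listed for HEFI-2019 scores | No |

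**Step 4: timing of the supplement term.** Supplements are reported in each recall, and neither 5.2.3 nor 7.5 says whether the covariate is the baseline value or the value at the time of the scan. If it is the latter, it is measured after randomisation. Adjusting for it could then remove or distort part of the arm difference. Fitting the same adjusted model without that one term shows how far the estimate depends on it.

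**Step 5: what a baseline exclusion can show.** Randomisation balances baseline supplement use in expectation. Excluding baseline users therefore shows whether existing users drive the result, but it leaves in anyone who starts later. A difference between arms arising during follow-up becomes visible only if use is tabulated by arm at each time point.

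**Step 6: the *no intake* rule.** The wording does not separate a completed recall listing no supplement from the absence of any recall. Section 7.5 sends missing covariates to full information maximum likelihood, but that applies only if the indicator is set to missing.

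**The case against.** The strongest reply is that the sentence is a harmless slip. Skin carotenoids keep the per-protocol and as-treated analyses and the general missing-data analyses. Adjusted and unadjusted estimates will both be reported. The main model already adjusts for supplements, and randomisation protects against baseline imbalance. Other outcomes, such as perceived income adequacy and subjective social status in section 7.6, have no sensitivity analysis beyond those of section 7.2, so deleting the sentence would leave carotenoids on the same footing. All of this stands. A reader might infer that the scan result has no robustness check at all; sections 6.2, 6.4 and 7.2 rule that out.

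It could also be said that HEI-2015 was meant as triangulation between self-report and scan. That does not rescue the sentence. A correlation between HEFI-2019 and the scan is already planned, and agreement between two measures does not test the arm difference in one of them.

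A second inference would be that the supplement rule counts everyone without a recall as a non-user. The SAP does not say so. The more natural reading presupposes a completed recall, and a participant without one could be coded as missing. The rule is unclear on this point, not shown to be wrong. Nor can a miscoding rate be derived, since the SAP gives neither the share of participants scanned without a recall nor the rate of supplement use.

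What the reply does not answer is that the SAP reserves one outcome-specific analysis for carotenoids, spends it on another endpoint, and leaves its own named threat with no dedicated check.

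**Conclusion.** The point holds in limited form. As written, the HEI-2015 analysis under Skin Carotenoids cannot test the carotenoid result, and it duplicates a check already planned where it belongs. The remaining analyses are useful, but none varies supplement handling on its own.

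The reach is small. Skin carotenoids are a secondary outcome that section 6.5 treats as supportive and hypothesis-generating. The main carotenoid model remains usable, and the primary A1C analysis is not touched. No numerical bias is claimed.

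The conclusion that the analysis is misdirected rests only on the data sources stated in 5.2.3 and needs no assumption. The case for a supplement-specific replacement rests on the SAP's own statement that supplements may raise skin levels. The case for the run without the supplement term is stronger if the covariate is taken at follow-up, which the SAP leaves open. Whether supplement use differed between arms is unknown.

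**What to change.** In section 7.5, replace the HEI-2015 sentence under Skin Carotenoids with:

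- (a) the same adjusted carotenoid model without the supplement term, because supplement use reported in follow-up recalls is measured after randomisation;
- (b) the carotenoid model excluding participants with a carotenoid-containing supplement in a baseline recall;
- a table of carotenoid-supplement use by arm at each time point, because (b) alone does not catch people who start supplements later.

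Keep the HEI-2015 analysis under HEFI-2019 as it is.

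As a minor clarification in section 5.2.3, apply *no intake* only when at least one recall was completed at that time point, and otherwise set the indicator to missing so that the covariate handling in section 7.5 applies.

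The cost is a few lines of SAP wording, two short model runs and one table, all from data already held. The downside is a slightly smaller sample in run (b).
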